### 12.3. Termination Procedures:

*This study may be temporarily suspended or prematurely terminated if there is sufficient reasonable cause. Written notification, documenting the reason for study suspension or termination, will be provided by the suspending or terminating party to the PI, IND/IDE sponsor and regulatory authorities. If the study is prematurely terminated or suspended, the PI will promptly inform the IRB and will provide the reason(s) for the termination or suspension. The study team will notify the participants of the study termination.*

## MEDICAL PROTOCOL (HRP-590)

PROTOCOL TITLE: Combining cerebellar tDCS and constraint-induced language therapy in non-fluent aphasia: a novel approach to target discourse

VERSION DATE: 08/09/2023

**Privacy/Confidentiality Risks:** *Risk of loss of confidentiality is unlikely, but could possibly occur as PHI is utilized as part of this study. This risk would be minimized by protections such as de-identification of participants via use of a study identifier, locked/secured/limited access to PHI, and electronic data securely stored and password-protected.* See also adverse events in 18.2

## MEDICAL PROTOCOL (HRP-590)

PROTOCOL TITLE: Combining cerebellar tDCS and constraint-induced language therapy in non-fluent aphasia: a novel approach to target discourse

VERSION DATE: 08/09/2023

13.2. Reproduction Risks: *Although there have been no adverse side effects of tDCS to women who are pregnant, all neuromodulation studies exclude this population due to unknown impact to an unborn baby.*

13.3. Risks to Others: N/A

## 14. Potential Benefits to Participants

14.1. Potential Benefits:

*There is a potential for a transient improvement in language expression and working memory after participating in the study.*

## 15. Statistical Considerations

15.1. Data Analysis Plan:

*All data will be de-identified and entered into Excel and SPSS for analysis. Visual analysis will be conducted initially with plotting of descriptive statistics.*

15.2. Power Analysis:

*A literature review of studies measuring the impact of cerebellar tDCS in aphasia did not find usable estimates of variation (SD, SEM, IQR, etc.) for the outcomes of interest. Accordingly, using a standard effect size scale (Cohen's d, scaling the treatment effect size relative to between-participant SD), and a range of plausible within-participant correlations of +0.4 to +0.9, we estimate that enrolling 4 participants will provide 80% power to detect large ( $d=0.9$ ) to very large ( $d=2.3$ ) treatment effect sizes using a two-sided 5% significance level.*

*A post-hoc power analysis will be conducted using the information gathered in the pilot study to determine the sample size needed for a larger study.*

15.3. Statistical Analysis:

*BDAC was consulted regarding the plan for statistical analysis.*

*Based on their recommendations, the following plan was created.*

*Throughout the project, BDAC will be consulted to review this statistical analysis plan and provide additional insight to alternative statistical processes best suited for the data as needed.*

*• The quantitative data for attrition rate and adverse events will be descriptive in nature and will be reported as counts and rates. The*

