## MEDICAL PROTOCOL (HRP-590)

PROTOCOL TITLE: Combining cerebellar tDCS and constraint-induced language therapy in non-fluent aphasia: a novel approach to target discourse

VERSION DATE: 08/09/2023

*to make a peanut butter sandwich". Each task has established standards and a scoring system for responses. Scoring is categorical and includes: accurate and complete =3, accurate and incomplete =2, inaccurate and complete =2, inaccurate and incomplete =1 and absent response =0 (Richardson & Dalton, 2016). Hypothesis: We hypothesize the raw score of each of the discourse measures (picture, story and procedure) will significantly increase after the real tDCS intervention, but not after the sham intervention.*

*2) Verbal Fluency is assessed by asking the participant to name as many animals as they can in one minute and then as many words that start with /f/ as they can in one minute. The tester collects a tally of how many animals and words that begin with /f/ were produced by the participant which is used as a raw score, scaled. If the participant names items that are not within those categories, those responses are not counted in the tally. These tasks are valid and reliable and used throughout aphasia literature.*

*Hypothesis: We hypothesize the raw score of the verbal fluency measures will significantly increase after the real tDCS intervention, but not after the sham intervention.*

*These data will be collected at four points in time:*

- 1) Initial baseline;
- 2) post intervention (A or B);
- 3) Follow-up baseline (after washout period);
- 4) post intervention (A or B)

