## 10. Local Number of Participants

10.1. Local Number of Participants to be Consented: *A total of 5 participants will be enrolled with the goal of 3 participants to complete the duration of this pilot study.*

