### 12.2. Withdrawal Procedures:

*If a participant wishes to withdraw or we determine that the participant should withdraw, we will terminate data collection and discuss with the participant the reasons for withdrawal. All data collected up to that point will be used in analysis unless the participant wishes for their data not to be used.*

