## MEDICAL PROTOCOL (HRP-590)

PROTOCOL TITLE: Combining cerebellar tDCS and constraint-induced language therapy in non-fluent aphasia: a novel approach to target discourse

VERSION DATE: 08/09/2023

*open-ended questions regarding barriers to participation will be analyzed to identify common themes.*

- Primary outcome measures, main concept discourse scores and verbal fluency counts, will be compared between treatment conditions using mixed effects generalized linear models, with fixed effects for treatment, period, sequence, pre-post time point, and treatment by pre-post time point interaction, and random effects for participant within sequence. This will provide difference-in-differences (post-treatment minus pre-treatment) estimates for the treatment effect which will be reported along with 95% confidence intervals as a measure of precision. Similar models will be used to analyze the secondary outcome measures including WI card sorting task, EEG delta wave, and SAQOLL.*
- Estimates from these models will provide important information for planning a well-powered clinical trial that are not obtainable elsewhere. Estimates that will be gathered in this pilot trial that will inform the subsequent power calculation include the treatment effect size, within-participant correlation of repeated measures, and random effects variance, for each of the outcome measures.*
- Pearson's Correlation will be conducted to determine the relationship between primary outcome variables (discourse and working memory scores) and SS-QOL as well as other scaled demographic variables such as age and duration since stroke.*
- Spearman's Rho Correlation analyses will be conducted to determine the relationships between primary outcome variables (discourse and working memory) and EEG data, reported in percentage.*
- The multivariate repeated measures and correlation analyses may not be terribly informative as the pilot sample size may lack the power for these statistics. However, they may be useful in descriptive interpretation of the data and lay the foundation for the larger clinical trial.*

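### The 80% power in 15.2 is computed for 4 participants, a number the design does not use; at the target of 3 completers it is about 51–55% for the planned model

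*Combined protocol and SAP*

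**What the plan says.** Section 15.2 reports that the literature gave no usable variance estimates. It therefore works with Cohen's d scaled to the between-participant SD, correlations of 0.4 to 0.9 and a two-sided 5% level, and concludes: "we estimate that enrolling 4 participants will provide 80% power to detect large" (d=0.9) to very large (d=2.3) effects. It names no test and no degrees of freedom, and does not mention dropout.

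Section 10.1 sets the size of the trial: "A total of 5 participants will be enrolled with the goal of 3 participants to complete the duration of this pilot study".

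Section 15.3 plans a mixed model on four assessments per participant (before and after each condition). It has fixed effects for treatment, period, sequence, time point and treatment by time point, and a random participant effect: "This will provide difference-in-differences (post-treatment minus pre-treatment) estimates for the treatment effect". The same section later warns, about multivariate repeated-measures and correlational analyses, that "the pilot sample size may lack the power for these statistics".

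Section 12.2 governs withdrawals: "All data collected up to that point will be used in analysis unless the participant wishes for their data not to be used". The hypotheses in 3.1 are that scores "will significantly increase after the real tDCS intervention, but not after the sham intervention".

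**The concern.** The power statement rests on 4 participants, while the trial plans for 5 at entry and 3 at completion. With so few participants one fewer matters a great deal, because the standard error rises and the t critical value rises steeply as degrees of freedom fall. A power figure for 4 therefore says little about a trial aiming for 3.

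The estimator matters too. A difference-in-differences of four measurements has twice the variance of a single paired difference, and 15.2 does not say which of the two it describes.

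What is at stake is interpretation. The hypotheses in 3.1 are phrased as significance after real stimulation and not after sham. A reader told that power was 80% for large effects could take a non-significant result as evidence that no large effect exists.

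**Working it through.** **Inputs.** From 15.2: two-sided 5%, d=0.9 to 2.3, r=0.4 to 0.9, n=4. From 10.1: 5 enrolled, 3 completers. From 3.1 and 15.3: four measurements per participant and the model above, which has 6 fixed-effect parameters with the intercept. Assumed, because not stated: d=2.3 goes with r=0.4 and d=0.9 with r=0.9; outcomes are Gaussian with equal correlation across visits; residual df are used. SD is set to 1.

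**Formulas.** Power is the upper tail of a noncentral t with noncentrality d/SE, beyond the 97.5% point of t on the given df.

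- Paired t-test: SE = √(2(1−r)/n), df = n−1.
- Planned model: each pre-to-post change has variance 2(1−r), so the difference of two changes has variance 4(1−r) and SE = 2√((1−r)/n). Residual df = 4n − 6 − (n−2) = 3n − 4. Generalised least squares on the actual design matrix confirmed both, including a 2:1 sequence split.

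**Reproducing the stated figure (n=4).**

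- Paired t, r=0.4: SE = √(1.2/4) = 0.548, noncentrality 2.3/0.548 = 4.20, df 3, power 79%.
- Paired t, r=0.9: SE = √(0.2/4) = 0.224, noncentrality 0.9/0.224 = 4.02, df 3, power 76%.
- The effects detectable with 80% power are 2.33 and 0.95, close to the stated 2.3 and 0.9.
- A difference-in-differences with a generous 4n−1 = 15 df gives 2.32 and 0.95, so the method behind 15.2 cannot be inferred.

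**Planned model at n=3.**

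- r=0.4: SE = 2√(0.6/3) = 0.894, noncentrality 2.57, df 5, power 55%.
- r=0.9: SE = 2√(0.1/3) = 0.365, noncentrality 2.46, df 5, power 51%.

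**Power at d=2.3 (r=0.4) / d=0.9 (r=0.9).**

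| Complete participants | Paired t (df n−1) | Planned model (df 3n−4) | Detectable d at 80%, planned model |
|---|---|---|---|
| 3 | 50% / 47% | 55% / 51% | 3.14 / 1.28 |
| 4 | 79% / 76% | 74% / 70% | 2.48 / 1.01 |
| 5 | 93% / 91% | 86% / 83% | 2.13 / 0.87 |

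**Other df choices for the difference-in-differences at n=3.**

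- Participant-level change-score differences, df 2: 31% / 29%.
- Generous 4n−1 = 11 df: 65% / 61%.
- Wald z: 73% / 69% nominally, but a 1.96 cut-off on 5 df has a true two-sided error of 10.7%.

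**Three completers plus two dropouts whose data are kept under 12.2 (planned model).**

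- First baseline only, 5 df: 51–57%.
- Full first period, 7 df: 72% / 69% with one dropout in each sequence; 69% / 66% with both in one sequence.
- First period and second baseline, 9 df: 71–78%, depending on sequence.

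Simulation agreed with the noncentral-t results for complete data and for two first-period dropouts, one in each sequence.

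**The case against.** The strongest reply is that three completers with nothing from the other two is not what the plan expects. Section 12.2 keeps data from withdrawn participants and a mixed model can use them. Two dropouts who each finish the first period bring power to 66–72%, close to the 70–74% for four completers, so the mismatch in numbers may cost little. This stands, and the 51–55% should be read only as the case of three completers alone. None of the partial-data cases reaches 80%, however.

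Second, the fall from 80% to 51–55% has two causes. The planned model gives only 70–74% even with 4 completers, so part of the gap comes from the estimator. Like for like, going from 4 to 3 lowers power from 76–79% to 47–50% (paired t) or from 70–74% to 51–55% (planned model). This also stands.

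Third, 15.2 claims 80% for 4, not for 3, and the figure is roughly reproducible; enrolment of 5 exceeds the powered number. That is fair: the calculation can be defended for n=4, and the fault is that it describes a sample the design does not use.

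Fourth, no df method, covariance structure or response distribution is given, and for the difference-in-differences with 3 completers the result ranges from 29% to 73%. That supports asking for the method to be named. The only calculation found that exceeds 80% with 3 is a normal approximation to the simple paired contrast (94–95%). It is not valid at this size and would give about 98% at n=4, so it is not the source of 15.2.

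Finally, this is a pilot with a feasibility aim, 95% confidence intervals are planned, and 15.3 concedes limited power. These limit the harm. Whether the concession covers the primary model is unclear. If it does, it sits badly with the 80%; if it does not, the 80% goes unqualified.

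**Conclusion.** The concern holds. The power statement uses 4 participants where the design has 5 entering and 3 expected to finish. At 3 completers only, power at the stated effects is 51–55% for the planned model and 47–50% for a paired t-test, not 80%. Retained partial data from two dropouts raises the planned model to between 51% and 78%, depending on how much they contribute; only completion by all five takes it past 80% (83–86%). The planned-model figures assume Gaussian outcomes, equal correlation across visits, residual df and the pairing of the larger d with the lower correlation. The conclusion that 3 completers fall short of 80% does not depend on the choice among the t-based methods. This should be corrected, but it does not undermine a pilot meant to supply estimates for a larger trial.

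**What to change.** Use one set of numbers in 10.1 and 15.2, giving enrolment and target completers separately, and name the test, df and correlation structure behind the power figure. Then restate 15.2 for the estimator in 15.3, for example:

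> With 3 completers the planned model (5 residual df, equal correlation across visits) has 80% power only for d of about 1.3 (r=0.9) to 3.1 (r=0.4). At d=0.9 (r=0.9) and d=2.3 (r=0.4) its power is 51–55%, about 66–72% if two dropouts each contribute a full first period, and 83–86% only if all 5 complete. A non-significant result is not evidence against a large effect.

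If the team intends another df method or covariance structure, it should state that and recompute these figures. The caveat in 15.3 should say whether it covers the primary model. The cost is wording in 10.1, 15.2 and 15.3 and a less favourable power statement; no extra enrolment is proposed.

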### 1. Objectives

#### 1.1. Purpose:

*To determine the effect of combining constraint-induced language therapy (CILT) with cerebellar tDCS in individuals with non-fluent aphasia after stroke.*

*The primary aims are to 1) determine the effect of combining cerebellar tDCS with constraint-induced language therapy (CILT) on language as measured by a verbal fluency task and discourse analysis task in a prospective, crossover study of adults with non-fluent aphasia after a cortical stroke and 2) demonstrate feasibility and data collection to inform a larger study.*

*The secondary aims include impact of the combined intervention on 1) resting state spectral EEG as measured through delta wave percentage 2) working memory as measured by the score on the Wisconsin Card Sorting Test and 3) quality of life as measured by the Stroke Aphasia Quality of Life survey tool. A final secondary aim will be to identify the tolerance of the intervention and barriers to participation measured by the adverse events questionnaire.*

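### Section 15.2 sizes the larger study by post-hoc power on 3 to 5 people, with the observed treatment effect among the inputs and no target difference or error allowance

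*Combined protocol and SAP*

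**What the plan says.** Section 15.2 closes its power statement by saying that a "post-hoc power analysis will be conducted using the information gathered in the pilot study to determine the sample size needed for a larger study". Section 15.3 describes what feeds that calculation: "Estimates that will be gathered in this pilot trial that will inform the subsequent power calculation include the treatment effect size", together with the correlation between a person's repeated scores and the random-effect variance, for every outcome. It adds: "Estimates from these models will provide important information for planning a well-powered clinical trial that are not obtainable elsewhere".

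On numbers, section 10.1 reads: "A total of 5 participants will be enrolled with the goal of 3 participants to complete the duration of this pilot study". Section 15.2 itself works with 4. Section 12.2 keeps the data of people who withdraw unless they object, so 3 to 5 people would contribute if the goal is met.

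The plan also shows caution. The literature review "did not find usable estimates of variation (SD, SEM, IQR, etc.) for the outcomes of interest", so the power statement uses "a range of plausible within-participant correlations of +0.4 to +0.9". Section 15.3 promises 95% intervals for the treatment effect and concedes: "The multivariate repeated measures and correlation analyses may not be terribly informative as the pilot sample size may lack the power for these statistics". The biostatistics centre (BDAC) is to be consulted throughout. Preparing for a larger study is part of a primary aim in section 1.1: "demonstrate feasibility and data collection to inform a larger study".

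**The concern.** Required sample size depends on (SD / effect) squared, so error in the effect is magnified when the effect is turned into a number of people. An effect estimated from 3 to 5 people carries an interval wider than most effects anyone would plan for. Sections 15.2 and 15.3 together allow that estimate to set the size of the next trial. The text does not rule out a worthwhile difference as the target, but it names none. It also gives no confidence limit, shrinkage or sensitivity range for the step.

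The pilot variance and correlation are a different matter. Section 15.2 found no usable outside estimates, so taking these from the pilot is reasonable if their uncertainty is carried forward. The weak input is the observed effect used as the target. At stake is whether the pilot can support the well-powered trial that section 15.3 mentions.

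**Working it through.** **The plan's own figure.** The documents give no size for the larger study. The pilot statement in 15.2 is 4 participants, 80% power, two-sided 5%, d = 0.9 to 2.3 for correlations 0.9 to 0.4. Read as a paired t-test with n = 4 and 3 df, the standardised effect is d / sqrt(2(1 - correlation)): 0.9 / sqrt(0.2) = 2.01 and 2.3 / sqrt(1.2) = 2.10. Power is 76.0% and 79.1%, and the effects detectable with 80% power are 0.95 and 2.33. This is close to the printed figures, and the point does not depend on it.

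**Precision under the planned model.** With n completers there are 4n scores and n + 4 fitted mean parameters (participants, treatment, period, time point, interaction; sequence is absorbed by participant). Residual df are 3n - 4: 5, 8 and 11. One person's difference-in-differences has variance 4 x sigma squared. In units of its SD, the 95% half-width is therefore t(0.975, df) / sqrt(n).

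**Size needed.** For an assumed standardised effect of 0.5, (1.96 + 0.84)^2 / 0.5^2 + 2 = 33.4, so 34 people; the exact noncentral t agrees. With 4 completers the standard error of the standardised effect is about 1 / sqrt(4) = 0.5. One standard error up gives an observed 1.0 and a plan of 7.84 + 2 = 9.84, or 10 people. One standard error down gives 0 and no finite plan.

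**Plug-in simulation.** One million pilots were simulated per case, with normal outcomes and complete data. The estimate is N(0.5, 1/n) in SD units and the variance is chi-squared(df) / df. Planned N is the formula above applied to the observed standardised effect. The wrong-sign share can be checked by hand as Phi(-0.5 x sqrt(n)).

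| Completers | df | 95% half-width | Wrong sign | Right sign, within 20% of 34 | Right sign, 17 or fewer | Right sign, 68 or more |
|---|---|---|---|---|---|---|
| 3 | 5 | 1.48 | 19% | 7% | 38% | 19% |
| 4 | 8 | 1.15 | 16% | 8% | 35% | 21% |
| 5 | 11 | 0.98 | 13% | 9% | 33% | 23% |

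The remaining 17-22% are right-signed with errors of intermediate size. Seventeen people would give 49% power.

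**Sensitivity to the model.** If treatment response varies between people, with variance up to 4 times the residual, the wrong-sign, within-20% and half-or-less shares are 13-19%, 7-9% and 33-39%. For a simple paired analysis (n - 1 df; half-widths 2.48, 1.59, 1.24) they are 13-19%, 6-8% and 36-42%.

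**Sensitivity to the assumed effect** (paired analysis, 4 completers):

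| Assumed effect | Needed | Planned N, 10th to 90th percentile | Plans with true power below 50% |
|---|---|---|---|
| 0.5 | 34 | 6 to no finite value | about 39% |
| 0.8 | 15 | 4 to 263 | about 37% |
| 2.0 | 5 | 3 to 8 | about 22% |

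**The case against.** The strongest reply is that the defect is conditional. Section 15.2 speaks of information from the pilot, and 15.3 uses the softer idea of informing the calculation, listing effect, correlation and variance together. Neither says that the observed effect will be the target. This stands, and it is why the conclusion is worded with an if. But the observed effect is a named input and no other target is offered.

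Next, the plan is not silent on imprecision. In 15.3 the estimates reported with 95% intervals are the same ones offered for planning, the small-sample caveat goes on to mention the larger trial, and BDAC stays involved. These links are real but general. None sets a target difference or a numerical allowance.

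Third, nothing in the pilot's own conduct or analysis changes, and the larger trial would need its own justification of size. That stands and limits the consequence.

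Fourth, the remedy leans on the variance allowance. With a fixed worthwhile difference equal to the assumed 0.5, the pilot variance point estimate alone still undersizes in 55-61% of pilots under the planned model. That is also correct, so the allowance is a necessary part of the fix.

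**Conclusion.** The point holds, and the text should be changed. If the observed effect is used as the target, the projected size is unreliable in both directions; in the 0.5 illustration fewer than one pilot in ten plans within 20% of need. The figures assume a true effect that the documents do not give, normal outcomes, complete data and 3 to 5 completers. Three is a goal, not a guaranteed minimum. At a very large true effect the spread is much smaller in numbers of people.

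A reader might infer three stronger things that the documents do not support:

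- **That the larger trial will be too small.** In the 0.5 case about 51% of all pilots plan too few people, roughly a third plan too many, and the rest have the wrong sign. The balance depends on the unknown true effect and on which pilots go forward, and the documents state neither.
- **That a primary aim fails.** Section 1.1 speaks of feasibility and data collection to inform a larger study and does not mention sample size. The feasibility, attrition and variance outputs are still delivered.
- **That the plan's d = 0.9 to 2.3 fixes the size of the problem.** Those are detectable effects, not expected ones. Converting them to the difference-in-differences scale needs assumptions that the plan does not state.

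**What to change.** In 15.2, replace the post-hoc power sentence with a statement that the larger trial's size will rest on a prespecified, justified worthwhile difference in main concept score and in verbal fluency. If none can yet be justified, say that required size will be tabulated over a stated range of target differences and not read from the pilot's point estimate.

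In 15.3, remove the treatment effect size from the inputs to the power calculation and report it with its 95% interval only. Keep the pilot variance and correlation as inputs, with an allowance for their uncertainty suited to the model fitted. For a normal outcome under the planned random-intercept model with no variation in treatment response, the one-sided 80% variance multiplier is df / chi-squared(0.20, df): about 2.1, 1.7 and 1.6 for 3, 4 and 5 completers. For a paired analysis it is 4.5, 3.0 and 2.4. A count model of verbal fluency needs a different method, such as a sensitivity range.

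The cost is a few sentences, the work of justifying two differences that the documents do not supply, and usually a larger projected size. In the 0.5 case, with the worthwhile difference equal to the true effect, the planned-model allowance gives a median of 47-61 people against 34 needed and undersizes in 19-25% of pilots (response variance 0 to 4 times the residual). The paired allowance gives a median of 66-100 and undersizes in about 20%. Visits, participants and the pilot's own analyses do not change.
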